2.5 Treatments (study treatment, rescue medication, concomitant therapies, compliance)

2.5.1 Study treatment / compliance

The analysis of study treatment data will be based on the safety set. The duration of exposure to study treatment will also be summarized by treatment group. In addition, the number and percentage of subjects with cumulative exposure levels (e.g. any exposure, ≥ 1 week, ≥ 2 weeks, ≥ 3 weeks, ≥ 4 weeks, ≥ 8 weeks, etc.) will be presented.

Duration of exposure of a treatment will be defined as the time from first dose of the treatment to the minimum of (last dose of the treatment + 84 days) and (last visit date).

Duration of exposure (years) = duration of exposure (days) / 365.25

Duration of exposure (100 subject years) = duration of exposure (years) / 100

The analyses of duration of exposure described above will be done for the entire study treatment period.

2.5.2 Prior, concomitant and post therapies

Prior and concomitant medications will be summarized in separate tables by treatment group.

Prior medications are defined as treatments taken and stopped prior to first dose of study treatment. Any medication given at least once between the day of first dose of study treatment and the date of within 84 days after last dose will be a concomitant medication, including those which were started pre-baseline and continued into the period where study treatment is administered.

Medications will be presented in alphabetical order, by Anatomical Therapeutic Classification (ATC) codes and grouped by anatomical main group. Tables will show the overall number and percentage of subjects receiving at least one treatment of a particular ATC code and at least one treatment in a particular anatomical main group.

Significant prior and concomitant therapies and procedures will be summarized by primary system organ class and MedDRA preferred term.

The number and percentage of subjects receiving prior and concomitant psoriatic arthritis therapy will be presented by randomized treatment group as well as the reasons for stopping their therapies (primary lack of efficacy, secondary lack of efficacy, lack of tolerability, other). The number and percentage of subjects receiving the following three categories of prior or concomitant medications will be summarized separately in one table: cDMARDs, MTX and non-MTX cDMARDs. This is the list of cDMARDs: Sulfasalazine, Leflunomide, Cyclosporine, Methotrexate, azathioprine, minocycline and apremilast.

Prohibited medication is defined in section 5.5.8 of the protocol.

The number and rates of subjects taking Prohibited medication will be presented.

2.6 Analysis of the primary objective

2.6.1 Primary endpoint

As the Primary objective of the study is to compare the efficacy of secukinumab **monotherapy** 300 mg s.c. with adalimumab **monotherapy** (40 mg s.c.) with respect to ACR20 at Week 52, the estimand of interest is the ACR20 response at week 52 in monotherapy patients who do not permanently discontinue study medication prematurely nor require rescue cDMARDS. The estimand will be evaluated in the FAS population by comparing the odds of response to each treatment (odds ratio). The primary efficacy endpoint is a composite endpoint. Clinical response, failure to permanently discontinue study medication prematurely, and lack of need for rescue medication will be required for a patient to achieve treatment success. The primary endpoint is the proportion of patients with **monotherapy** ACR20 response at Week 52 where **monotherapy** ACR20 response is defined as meeting the following three conditions:

- achieving American College of Rheumatology 20 (ACR20) response
- no permanent study treatment (Secukinumab or adalimumab) discontinuation before or at Week 50 (the last dosing visit)
- no use of cDMARDS (including MTX) after week 36 (regardless of the starting time of taking cDMARDS)

A patient who does not meet any of the three conditions above is regarded as a monotherapy non-responder.

The list of possible cDMARDS for criterion 3 are the following: sulfasalazine, leflunomide, cyclosporine, methotrexate, azathioprine, minocycline and apremilast.

The analysis of the primary efficacy endpoint will be based on the FAS subjects. Primarily, CRP will be used instead of ESR to calculate ACR response; ESR will only be used in the event CRP is missing.

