5.5.6 Rescue medication

Rescue medication is defined as any new therapeutic intervention or a significant change to ongoing therapy made because a subject is experiencing either no benefit from participation in the trial or worsening/exacerbation of their disease.

Rescue medication must not be used before completion of Week 52 assessments (see Section 3.1). Please see Section 5.5.7 and Section 5.5.8 for details. Although no subject will be restricted from receiving necessary rescue medications for lack of benefit or worsening of disease, subjects will be discontinued from investigational treatment if treated with prohibited medications (as described in Section 5.5.8). Subjects who discontinue investigational treatment can continue to attend all subsequent scheduled visit assessments unless informed consent is withdrawn. If study investigational treatment is discontinued, subjects may take study prohibited medication under the investigator's guidance and per locally approved prescribing information.

Efficacy and safety will be assessed in detail at every study visit and subjects who are deemed by the investigator not to be benefiting from study treatment, or for any reason on the subject's own accord, will be free to discontinue study participation at any time.

Use of rescue medication must be recorded on the corresponding eCRF.

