5.5.9 Discontinuation of study treatment

Subjects may voluntarily discontinue study treatment or the study for any reason at any time. The investigator should discontinue study treatment for a subject if, on balance, he/she believes that continuation would be detrimental to that subject's well-being.

Study treatment must be discontinued under the following circumstances:

- Withdrawal of informed consent
- Subject's request to terminate treatment
- Emergence of the following AEs:
- 1. Any severe or serious AE that requires treatment with an unacceptable co-medication
- 2. Onset of lymphoproliferative disease or any malignancy except for treated basal cell carcinoma, treated actinic keratosis, treated in situ carcinoma of the cervix, or non-invasive malignant colon polyps which are being or have been removed
- 3. Life-threatening infection
- Severe hypersensitivity reaction or anaphylactic reaction
- Any laboratory abnormalities that in the judgment of the investigator are clinically significant and are deemed to place the subject at a safety risk for continuation in the study (a general guidance on clinically notable laboratory values is provided in Appendix 7)
- Pregnancy
- Use of prohibited treatment as per Table 5-2 and in particular addition of concomitant cDMARD (e.g. MTX). Subjects who discontinue study treatment but continue to attend scheduled visits may use prohibited medications under the guidance of the study Investigator.
- Any other protocol deviation that results in a significant risk to the subject's safety

In addition to these requirements for study treatment discontinuation, the investigator should discontinue study treatment for a given subject if there is a lack of improvement or worsening of their symptoms, or if on balance, the investigator believes that continuation would be detrimental to the subject's well-being.

For subjects who discontinue study treatment, a Dosage Administration Record eCRF should be completed, giving the date and primary reason for stopping study treatment.

The appropriate personnel from the site and Novartis will assess whether study treatment should be discontinued for any subject whose treatment code has been broken inadvertently for any reason.

Subjects who discontinue **study treatment** should NOT be considered withdrawn from the study and can continue to attend all subsequent scheduled visit assessments, except if informed consent is withdrawn.

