9.4.3 Handling of missing values/censoring/discontinuations

The primary and secondary estimands focus on the difference between the treatment groups in the proportion of patients achieving monotherapy ACR20 response (or other response variables) at week 52 in FAS patients. Monotherapy response is defined as achieving the requirements for the clinical response (e.g. ACR20) and not prematurely discontinuing study medication and not taking concomitant MTX/cDMARD (composite estimands). Missing data for ACR20 response and other binary efficacy variables (e.g. ACR50, , PASI90, etc.) for data up to Week 52 will be handled by multiple imputation. Multiple imputation (MI) is a simulation based approach where missing values are replaced by multiple Bayesian draws from the conditional distribution of missing data given the observed data and covariates, creating multiple completed data sets. These completed data sets can then be analyzed using standard

methods. Within this analysis the ACR composites or PASI score will be imputed and response variables will be derived based on the imputed scores. In the multiple imputation analysis the response status will be imputed based on the individual treatment arm information.

Continuous variables (e.g. ACR components, DAS, etc.) will be analyzed using a mixed-effects repeated measures model (MMRM) which is valid under the missing at random (MAR) assumption. For analyses of these parameters, if all post-BSL values are missing then these missing values will not be imputed and this subject will be removed from the analysis of the corresponding variable, i.e. it might be that the number of subjects providing data to an analysis is smaller than the number of subjects in the FAS.

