Data will be analyzed by Novartis according to the data analysis section 9 of the clinical study protocol. The statistical methodology is described below and any deviations from the protocol are documented. Additional detailed information regarding the analysis methodology is contained in the Appendix section.

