2.6.3 Handling of missing values/censoring/discontinuations

Missing data

Patients who were unblinded prior to the scheduled timepoint will be considered non-responders from the time of unblinding up to Week 52.

Missing data for ACR20 response and other binary efficacy variables (e.g. monotherapy response of ACR50, ██████████, PASI90, etc.) for data up to Week 52 will be handled by Multiple Imputation (MI) if a subject neither discontinues the study treatment prematurely nor takes cDMARDs after week 36 but still has missing value for ACR20 (e.g., misses some visits). Details of the implementation is in [Section 6.2.2.4](#).

[figure not shown]
Multiple imputation (MI) is a simulation based approach where missing values are replaced by multiple Bayesian draws from the conditional distribution of missing data given the observed data and covariates, creating multiple completed data sets. These completed data sets can then be analyzed using standard methods. Within this analysis the ACR composites or PASI score will be imputed and response variables will be derived based on the imputed scores. In the multiple imputation analysis the response status will be imputed based on the individual treatment arm information.

[figure not shown]
Missing data for continuous efficacy endpoints due to missed or skipped visits will not be applied MI. Continuous variables (e.g. ACR20 components) will be analyzed using a mixed-effects repeated measures model (MMRM) which is valid for addressing missing value under the missing at random (MAR) assumption. As such, single-point imputation of missing data will not be performed (e.g. LOCF) nor employing MI. Details of the implementation is in [Section 6.2.1.2](#).

For analysis based on subset of subjects (i.e. Psoriasis, Enthesitis ██████████), a subject with missing baseline values will be excluded in the analysis.

For use of cDMARDs (including MTX) after Week 36, the start date and end date of cDMARDs use will be compared to the upper limit of the Week 36 analysis visit window (day 274). For partial or missing dates the following imputation rule will be used:

- If only date is missing (month and year are present), then for Concomitant Medication start date, use the first day of the month, for end date, use the last day of the month.
- If both month and date are missing, then for Concomitant Medication start date, use January 1st of the year, for end date, use December 31st of the year.

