Sources: The value for Secukinumab is from the lower bound of 80% confidence interval of a meta-analysis based on FUTURE2 and unpublished results from FUTURE3 data, the values for other endpoints for Secukinumab are from the means of the same meta-analysis, the values for Adalimumab are from Humira® study ([Gladman 2007](#)).

Based on [Table 3-1](#), power calculation for superiority tests of different endpoints are presented below in [Table 3-2](#).

[figure not shown]
Table 3-2 Power for superiority tests for primary and secondary endpoints (two-sided, $\alpha=0.05$)

[figure not shown]
Endpoint	Power*
ACR20 (H1)	94%
PASI90 (H2)	99%
ACR50 (H3)	91%
HAQ-DI (H4)	99%
Resolution of enthesitis (H5)	99%

* power does not consider dependence of the endpoints in the Testing Strategy, power for PASI90 and enthesitis is based on the assumption that a subset of half of the population (213 subjects per group) has data of these two endpoints.

4 Change to protocol specified analyses

All the analysis specified in the protocol for CSR is detailed in this SAP.

6 Appendix

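### The SAP's Day 274 limit on cDMARD use is not declared against protocol 9.4.3, and the imputation steps do not reliably apply the SAP's own rule at Week 52

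*SAP*

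**What the plan says.** **Protocol.** Section 9.4.3 defines monotherapy response as the clinical response "and not prematurely discontinuing study medication and not taking concomitant MTX/cDMARD (composite estimands"). No period is attached to the cDMARD condition. Section 5.5.9 lists among the mandatory reasons for stopping study drug "Use of prohibited treatment as per Table 5-2 and in particular addition of concomitant cDMARD (e.g. MTX"), and 5.5.6 adds that "Rescue medication must not be used before completion of Week 52 assessments".

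**SAP, rule.** Section 2.6.1 makes the third condition for the primary endpoint "no use of cDMARDS (including MTX) after week 36 (regardless of the starting time of taking cDMARDS"), and a patient who fails a condition is a non-responder. Section 2.6.3 says cDMARD start and end dates "will be compared to the upper limit of the Week 36 analysis visit window (day 274"). It allows multiple imputation only "if a subject neither discontinues the study treatment prematurely nor takes cDMARDs after week 36 but still has missing value for ACR20". Section 2.7 applies the same cDMARD condition to PASI90, ACR50 and enthesitis.

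**SAP, steps.** Section 6.2.2.4 (Details of Implementation) sets values recorded after late cDMARD use to missing (Step 2), imputes (Step 3), and then assigns non-response to visits later than the one at which the patient took the cDMARD (Step 6). The enthesitis list does the same in its Steps 2, 3 and 5. Step 5 (enthesitis Step 4) treats visits after the End of Treatment visit in the same way.

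**SAP, changes.** Section 1 says that "any deviations from the protocol are documented". Section 4, the place for changes, says only: "All the analysis specified in the protocol for CSR is detailed in this SAP".

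**The concern.** The rule decides the primary endpoint (H1) and also feeds H2, H3 and H5. Three things look wrong.

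- The SAP's condition is narrower than the protocol's, and Section 4 does not say so.
- The implementation steps are not equivalent to the rule. They impute patients whom 2.6.3 excludes from imputation, then rely on an undefined visit to turn the result back into non-response. Two programmers could both follow 6.2.2.4 and classify the same patient differently at Week 52.
- Every patient has had a cDMARD (inclusion criterion 9). Under 2.5.2, whether a drug is prior or concomitant depends on its stop date. The 2.6.3 rule for incomplete stop dates always picks the latest possible date, so it can fail a patient who completed washout.

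**Working it through.** **1. Reproduce the cut-offs.** SAP 6.1 gives upper limit = 0.25 × 7 × current week + 0.75 × 7 × next applicable week + 1.

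- Week 36, ACR components: 0.25×252 + 0.75×280 + 1 = 63 + 210 + 1 = 274. This matches 2.6.3.
- Week 48, ACR (next visit Week 52): 84 + 273 + 1 = 358, so the ACR Week 52 window opens on Day 359.
- Week 40, PASI/LEI (next visit Week 52): 70 + 273 + 1 = 344, so the PASI/LEI Week 52 window opens on Day 345.
- Scheduled days: Week 50 = 351, Week 52 = 365. Day 274 is 365 − 274 = 91 days before Week 52.

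**2. Protocol against SAP.** A patient who takes a cDMARD on Days 100–200 only and stays on study drug is a non-responder under 9.4.3 but can be a responder under 2.6.1. If study drug is stopped, as 5.5.9 requires, the discontinuation condition makes the patient a non-responder under both.

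**3. SAP rule against SAP steps.** Step 6 can be read in three ways:

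- The visit is the last one before the cDMARD start. Week 52 fails, as 2.6.1 requires.
- The Day 274 reference in the step is the anchor. Week 52 fails.
- The start date is placed in a Table 6-1 window. Week 52 fails only if the start falls in an earlier window.

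The third reading, for a patient on schedule (last dose Day 351, Week 52 assessment Day 365):

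| cDMARD start | 2.6.1/2.6.3 | ACR20, ACR50 | PASI90, enthesitis |
|---|---|---|---|
| Days 352–358 (7 days) | fail | Week 48 window, so fail | Week 52 window, so imputed value stands |
| Days 359–364 (6 days) | fail | Week 52 window, so imputed value stands | Week 52 window, so imputed value stands |

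That leaves 6 exposed start days for ACR and 7 + 6 = 13 for PASI/LEI. Starts on Days 345–350 also lie in the PASI/LEI Week 52 window, but a dose is still due then, so mandatory discontinuation should already make the patient a failure.

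**4. Step 5.** By week label, a stop at Week 50 fails Week 52. By window, Day 351 lies in the ACR Week 48 window and fails, but it already lies in the PASI/LEI Week 52 window and does not. A Week 50 visit 8 days late (351 + 8 = 359) reaches the ACR Week 52 window too. SAP 6.1 itself expects visit delays to accumulate.

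**5. Incomplete stop dates.** A year-only stop becomes 31 December. With first dose on 1 April as Day 1, Day 274 is 273 days later, 30 December, in ordinary and leap years, so 31 December counts as late use for any first dose up to 1 April. The stop must be in the same calendar year as first dose. A stop on 1 January plus the 4-week washout gives 29 January as the earliest first dose. The exposed first-dose dates are therefore about 29 January to 1 April. A wholly missing stop date is taken as ongoing, whatever the date of first dose.

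**6. Size per patient.** Arm sizes are the SAP Section 3 figures: 425, and 213 assumed for PASI90 and enthesitis.

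- ACR20/ACR50: 1/425 = 0.24 points. PASI90/enthesitis: 1/213 = 0.47 points.
- Average contribution of one wrongly imputed patient, assuming imputation at the Table 3-1 rates: ACR20 0.50/425 to 0.62/425 = 0.12 to 0.15 points; PASI90 0.38/213 to 0.63/213 = 0.18 to 0.30; enthesitis 0.33/213 to 0.61/213 = 0.15 to 0.29.

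**The case against.** The case against a larger finding is good, and most of it stands.

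- *The window reading is not written down.* Table 6-1 maps visits and assessments; no passage maps medication dates to it, and 2.6.3 makes a plain date comparison with Day 274. A reader might infer that the SAP will count late cDMARD users as responders. The documents do not support that: 2.6.1 states the outcome outright, and two of the three readings of Step 6 deliver it. What stands is that the steps do not secure the rule.
- *Step 5's own example uses week labels.* On that reading a Week 50 stop fails Week 52. The visit still needs a definition, because the windows give another answer for PASI/LEI.
- *Early users are mostly caught.* A reader might infer that cDMARD use before Day 274 is generally forgiven. Protocol 5.5.9 prevents this unless study drug was continued in breach of it.
- *A sensitivity analysis exists.* Protocol 9.4.4 already foresees one on cDMARD use alongside study drug. This softens the undeclared window but does not declare it.
- *A reason may be given elsewhere.* Parts of the SAP are not in the public copy, so the point rests on Section 4 not listing the difference.
- *The two discontinuation cut-offs.* Section 2.6.1 counts stops before or at Week 50; 2.7 counts stops before Week 52. A reader might infer that a stop on Days 352–364 passes ACR20 but fails ACR50. The protocol glossary defines discontinuation as stopping before the treatment completion date, and no dose remains after Week 50, so the difference is essentially one of wording.

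**Conclusion.** The point holds as a minor one. The SAP's cDMARD window differs from protocol 9.4.3 and Section 4 does not declare it. The 6.2.2.4 steps do not guarantee the Week 52 non-response that 2.6.1 requires and 2.6.3 protects from imputation. The stop-date rule can, rarely, fail a patient who washed out properly.

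The exposed-day counts assume on-schedule visits and the window reading of Step 6. A 91-day look-back may be defensible, but it is a choice that should be visible.

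The documents give no rate of cDMARD use, so neither the number affected nor the direction can be derived. Protocol 5.5.6 and 5.5.9 suggest the number is small. A reader might infer a bias towards one arm, or an effect on power or type I error; nothing in the documents supports either, and none is claimed.

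**What to change.** 1. Derive Week 52 non-response for H1, H2, H3 and H5 from one date-based flag: permanent discontinuation, or qualifying cDMARD use, before the Week 52 assessment (before Day 365 if that assessment is missing). Apply it whatever the analysis-visit window. State openly that this adds an end date: 2.6.1 has none, so on its literal wording first use in follow-up also counts. Rewrite Steps 2, 5 and 6, and enthesitis Steps 2, 4 and 5, to match, and define the End of Treatment visit.
2. Reconcile the cDMARD window with protocol 9.4.3, or declare the Day 274 window and its reason in SAP Section 4. Use the other version as the cDMARD sensitivity analysis foreseen in protocol 9.4.4.
3. For a cDMARD begun before first dose with documented washout, cap an incomplete stop date at the day before first dose.
4. As a wording tidy-up only, use one discontinuation cut-off in 2.6.1 and 2.7.

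The cost is some SAP wording and one derived flag before database lock. Only endpoint derivation changes; permitted treatment, visits and sample size do not.

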2.6.2 Statistical hypothesis, model, and method of analysis

The statistical hypothesis for monotherapy ACR20 is that there is no difference in the proportion of subjects fulfilling the monotherapy ACR20 criteria at Week 52 in the secukinumab 300 mg group vs. adalimumab.

Let p_j denote the proportion of monotherapy ACR20 responders at Week 52 for treatment regimens j , $j=0, 1$ where

0 corresponds to adalimumab,

1 corresponds to secukinumab 300 mg

In statistical terms, $H_0: p_1 = p_0$, $H_{1A}: p_1 \neq p_0$, i.e.

H_1 : secukinumab is not different to adalimumab regimen for signs and symptoms (monotherapy ACR20 response) at Week 52.

The primary endpoint of monotherapy ACR20 at Week 52 in the FAS will be evaluated using a logistic regression model with treatment as a factor and weight as a covariate. Odds ratios will

be computed for comparisons of secukinumab 300 mg vs. adalimumab regimen utilizing the logistic regression model fitted.

